## 4.3 Study period and end of study

- Expected recruitment rate: 1 patient/ month
- Expected enrollment duration of the study: 24 months
- Expected follow-up period: 12 months after the last patient accrual.
- Proposed extension of study timeline to 2022/12/13 for complete recruitment, follow-up, and analysis
- Expected total patient accrual: 30 patients
- End of study:
  - This will be a 2-stage study design based on the method proposed by Simon et al. The first stage will recruit 13 patients including 6 patients in the phase Ib part. If 0 patients had any objective response, the study will be unlikely to meet the pre-determined endpoint, and thus will be terminated early. If one or more patients had objective response, a total of 30 patients could be recruited.
  - The study may also terminate early if the combination is too toxic, i.e. that there are more than 2 patients met the DLT criteria in the lowest pre-determined combination dose (detail see Figure 2) in phase Ib part.

[figure not shown]

Figure 1. The schema of the study

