- f Tumor assessment by CT or MRI will be carried out on week 8, week 16, week 24, and every 12 weeks afterwards with a +/- 7 days window. The week 8 and week 24 images will be sponsored by the study and week 16 and images after week 24 will be performed according the National Health Insurance Payment system. If a patient reached CR or PR according to RECIST on the 8-, 16-, or 24-week cycle, a confirmed imaging more than 4 weeks later will be sponsored by the study.
- g 12-Lead ECG will be performed before every cycle to monitor the QTc for the first 4 cycles, then every 9 weeks afterwards.
- h The first biopsy will be performed within 4 weeks of treatment starts, the second biopsy will be taken after 1st tumor assessment. At least 10 patients are required to take the pre-treatment biopsy and the second biopsy after treatment is optional but strongly suggested.
- i Survival follow-up interval is 8 weeks +/- 1 weeks for at least 6 months or death
- j If in later cycles patient is using only lenvatinib as single agent treatment, D8 visit and blood test could be omitted
- k two eribulin injections should be at least  $\geq 5$  days apart

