## 7 Endpoints for Evaluation

### 7.1 Primary endpoint: Objective response rate (ORR) by RECIST 1.1

- Complete response (CR): the disappearance of all known disease, determined by two observations not less than 4 weeks apart.
- Partial response (PR): A 30% or greater decrease in the sum of LD of all lesions in reference to the baseline sum LD. In addition, there may be no appearance of new lesions or progression of any lesion.
- Stable disease (SD): Neither sufficient increase to qualify for PD nor sufficient shrinkage to qualify for PR.
- Progressive disease (PD): A 20% or greater increase in the sum of LD of all target lesions, taking as reference the smallest sum LD recorded at or following baseline.
- Once a patient reached PR or CR of his/her tumor assessment, another image will be done 4weeks later. A confirmed PR or CR is defined as both these image tumor assessment is in the same category (PR or CR).
- An ORR is defined as the either a CR or PR as defined by RECIST 1.1
- The best response as defined by RECIST 1.1 will be used for ORR assessment. The best response is defined as the most proximal response assessment before disease progression. If the first response evaluation showed disease progression, then the best response is PD.

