## **8 Statistical Considerations**

### **8.1 Sample size**

The study will be based on a minimax Simon 2 stage design. The ORR of interest with lenvatinib and eribulin combination is 20% (P1), and the ORR of low interest is set at 5% (P0). With an 80% power and type I error of 0.05, if no patients had an objective response to lenvatinib and eribulin combination after the first 13 enrollments, the trial will be stopped early for futility. If at least one patient had an objective response, the study will continue to include 27 evaluable patients. With an expected 10% drop-out rate, we estimate a total of 30 patients to be enrolled in this study.

If no dose de-escalation is needed in the phase Ib part, the 6 patients will be considered eligible to be included in the phase II part statistical analysis. If a lower dose is selected as the dose to go forward, only patients with the same dose as the phase II part will be included in the phase II statistical part.

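### Section 7.1 orders a confirmation scan but does not require confirmation for ORR, and its best-response rule can count a failed PR and drop a confirmed one

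*Combined protocol and SAP*

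**What the plan says.** Section 7.1 defines the phase II primary endpoint, and section 6.3.1 repeats its response categories and confirmation rule.

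- CR needs two observations at least 4 weeks apart. PR needs a 30% fall in the sum of diameters, with no second observation.
- After a PR or CR, another image follows 4 weeks later. "A confirmed PR or CR is defined as both these image tumor assessment is in the same category (PR or CR").
- The endpoint bullet reads "An ORR is defined as the either a CR or PR as defined by RECIST 1.1".
- The last bullet of 7.1 says that best response feeds the ORR, and defines it as the assessment closest to, and before, progression.

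Footnote f of the flow sheet in section 6.5 pays for the second scan after a response at week 8, 16 or 24: "a confirmed imaging more than 4 weeks later will be sponsored by the study".

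The stage 1 rule in section 4.3 reads "If 0 patients had any objective response, the study will be unlikely to meet the pre-determined endpoint". Section 8.1 repeats the rule without mentioning confirmation. It also does not say whether its 5% and 20% are confirmed rates. Section 8.2.1 adds only descriptive statistics and confidence intervals. Under section 6.3.2, response is read by the investigator.

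**The concern.** The plan defines a confirmed response and orders the scan needed to establish it, but no counting rule uses the result. This affects the primary endpoint of an open-label, single-arm trial in which the documents provide only for investigator reading. A single reading just past the 30% cut-off is where measurement error most easily creates a responder. Few responders are needed: one among 13 passes stage 1, and the stated design implies that four among 27 succeed. One patient more or less moves the ORR by 1/27 = 3.7 percentage points. Two analysts could follow 7.1 in good faith and report different ORRs from the same scans.

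**Working it through.** **1. The literal rule applied to two patients.** Set the baseline sum to 100. A sum of 69 is a fall of 31%, so PR. With 69 as the smallest sum, PD begins at 69 × 1.20 = 82.8. A sum of 78 is 22% below baseline and 78/69 = 1.13 times the smallest sum, so SD.

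| | Week 8 | Week 12 (confirmation) | Week 16 | Week 24 | Last assessment before PD | Counted in ORR? | Confirmed? |
|---|---|---|---|---|---|---|---|
| Patient A | 69 (PR) | at least 82.8 (PD) | – | – | PR | Yes | No |
| Patient B | 69 (PR) | 69 (PR) | 78 (SD) | at least 82.8 (PD) | SD | No | Yes |

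The literal rule classifies both patients opposite to the plan's own confirmation test.

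**2. The plan's own design.** Inputs from section 8.1: "The study will be based on a minimax Simon 2 stage design", P0 = 5%, P1 = 20%, "With an 80% power and type I error of 0.05", 13 patients in stage 1 with a stop at 0 responses, 27 evaluable and 10% drop-out. Sidedness is not stated; one-sided is assumed. The final cut-off is not printed. An exact search for the smallest N that meets these limits gives 0/13 and 3/27, that is, success at 4 or more of 27.

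For a counted response rate p:

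- P(pass stage 1) = 1 − (1 − p)^13
- P(success) = Σ over x = 1 to 13 of P[Bin(13, p) = x] × P[Bin(14, p) ≥ max(0, 4 − x)]

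At p = 5%, P(success) = 0.0416 and P(pass stage 1) = 1 − 0.513 = 0.487. At p = 20%, P(success) = 0.801. Enrolment is 27/(1 − 0.10) = 30. The plan's 13, 27 and 30 reproduce.

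**3. Effect of counting unconfirmed responses (illustration).** The documents give no rate of failed confirmation. Assume that a fraction f of single-scan responses fails, with f from 10% to 40%.

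- If 5% is the confirmed rate but single-scan responses are counted, the counted rate is 5%/(1 − f).
- If 20% was meant as a single-scan rate but only confirmed responses are counted, the rate is 20% × (1 − f).

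| f | Counted rate, 5%/(1 − f) | P(success) | P(pass stage 1) | Confirmed rate, 20% × (1 − f) | Power |
|---|---|---|---|---|---|
| 0 | 5.0% | 4.2% | 48.7% | 20% | 80.1% |
| 10% | 5.6% | 5.7% | 52.4% | 18% | 72.4% |
| 20% | 6.3% | 8.1% | 56.8% | 16% | 62.9% |
| 30% | 7.1% | 11.8% | 61.8% | 14% | 51.8% |
| 40% | 8.3% | 17.6% | 67.7% | 12% | 39.5% |

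These figures count every single-scan response. The last-assessment rule would remove a PR followed by SD and then PD. It would also remove confirmed responders such as patient B. Its net effect cannot be computed from the documents.

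**The case against.** The confirmation bullet sits in the primary-endpoint section, directly above the ORR bullet, and the ORR bullet defers to RECIST 1.1. A confirmed ORR may well be what the sponsor intends. That is fair, and it makes the defect one of wording rather than of proven intent. It does not remove it, because no counting rule refers to confirmation.

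Three stronger readings are tempting, and the documents do not support them.

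- *Every single-scan PR counts.* A reader might infer that 69 at week 8 and 78 at week 12 makes a responder. Once PD follows, the last assessment before it is SD, so that patient is not counted. A lone PR clearly counts when PD comes next.
- *A PR that deepens to CR is lost.* The same-category wording can mean PR/PR or CR/CR only, or that both scans show a response. On the strict meaning the label would be withheld, but the label does not feed the ORR as written, so nothing is lost unless confirmation becomes part of the endpoint. The amended text must settle this.
- *The type I error is really inflated.* If 5% and 20% are on the same basis as the responses counted, it stays at 4.2%. A figure as high as 27.1% needs a counted rate of 10% against a confirmed 5%, so that half of the counted responses fail confirmation. Nothing in the documents supports that.

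A practical objection also stands in part. The current version dates from May 2022 and the extended timeline ends in December 2022, so changing the primary endpoint this late in an open-label trial is more than a wording edit.

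**Conclusion.** The point holds as a defect in the primary endpoint. The ORR bullet does not require the confirmation that the plan defines and orders a scan for. The best-response rule can count a PR that failed confirmation and discard one that passed. The stage 1 rule inherits the gap.

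The contradiction rests on the text alone. The size does not: an increase from 4.2% to between 5.7% and 17.6% for a false positive, and from 49% to between 52% and 68% for passing stage 1, depends on the derived boundary of 4 of 27, on 5% being a confirmed rate, and on the assumed 10% to 40% failure. It shows how sensitive the design is and is not an estimate for this trial.

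**What to change.** - In 7.1 and 6.3.1, define ORR as the proportion of patients with a confirmed CR or PR: CR or PR on two assessments at least 4 weeks apart, with PR followed by CR counting as confirmed. Use the same definition for the response in 4.3 and 8.1.
- Replace the last-assessment rule with best confirmed response from treatment start to progression. Changing the ORR bullet alone would leave the two rules in conflict for patient B.
- Count patients without a confirming scan as non-responders.
- State in 8.1 that 5% and 20% are confirmed rates, and print the final cut-off.
- Report unconfirmed ORR as a sensitivity analysis.
- Align the interval, which is 4 weeks in 7.1 and more than 4 weeks in footnote f, to at least 4 weeks.

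Cost: N and the scan schedule do not change, since 7.1 already orders the scan. Footnote f funds it only for responses at weeks 8, 16 and 24, and the budget in section 10.3 has no line for it, so funding for later responses should be checked. The reported ORR may be lower. If 20% was meant as a single-scan rate, power falls to 72.4% at a confirmed rate of 18% and to 39.5% at 12%. Because the change comes late, the amendment should be dated and both ORRs reported.

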	
quantity of tumor infiltrating lymphocyte (TILs) is associated with increased response to chemotherapy or improved prognosis. One of the factors that had been shown to impede the migration and trafficking of TILs into tumor is vascular endothelial growth factor (VEGF). In renal cell carcinoma, treatment with bevacizumab, an anti-VEGF antibody, or in combination with atezolizumab, increased the recognition of tumor antigen, increased expression of MHC class I receptor on tumor cells, and the amount of TIL migration into the tumor stroma. Many of the STS were detected with scarce TILs in the tumor microenvironment ([name] et al. unpublished data), thus it would be interesting to see if anti-angiogenic tyrosine kinase inhibitors could adjust the tumor microenvironment toward a more chemotherapy-friendly milieu.
 
Thus, we would like to propose a clinical trial to understand the anti-tumor activity of the combination of lenvatinib and eribulin in advanced STS patients.

Objectives and Endpoints
	
Primary objective To evaluate the anti-tumor activity of lenvatinib and eribulin combination in STS.
 
Primary endpoint for phase Ib The safety profile of the combination of lenvatinib and eribulin
 
Primary endpoint for phase II The objective response rate (ORR) based on RECIST 1.1.
 
Secondary objectives and endpoints
 
 
● 24-week progression-free survival (PFS) rate
 
● 6- and 12-months overall survival (OS) rate
 
● PFS
 
● OS
 
● Safety profile of the combination of lenvatinib and eribulin
 

Study Design
	
Open-label single arm phase Ib/II study

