## 2 Objectives and Endpoints

Objectives and related endpoints are described in Table 1 below.

Table 1 Objectives and related endpoints

Objectives	Endpoints	Definition and analysis
Primary (phase Ib)		
To evaluate the safety of lenvatinib and eribulin combination in STS	Dose limiting toxicities (DLT)	Refer to section 5.3
Primary (phase II)		
To evaluate anti-tumor activity of lenvatinib and eribulin combination in STS	Objective Response Rate (ORR)	Refer to Section 7.1
Secondary (phase II)		Refer to Section 7.2
To evaluate the disease control ability of lenvatinib and eribulin in STS	(Progression-free survival) PFS rate at 24- weeks	Refer to Section 7.2.1
	Overall survival rate at 6- and 12-months	Refer to Section 7.2.2
	PFS and OS	Refer to Section 7.2.3
To evaluate the safety dose combination of lenvatinib and eribulin in STS	Incidence, type, intensity, severity and seriousness of Adverse Events (AEs) and frequency of dose interruptions	Refer to section 7.2.4
To evaluate anti-tumor activity of lenvatinib and eribulin combination in STS using other assessment method	Objective Response Rate (ORR) by Choi criteria	Refer to section 7.2.5

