### 4. Evaluations included following the RECIST 1.1

- Complete response (CR): the disappearance of all known disease, determined by two observations not less than 4 weeks apart.
- Partial response (PR): A 30% or greater decrease in the sum of LD of all lesions in reference to the baseline sum LD. In addition, there may be no appearance of new lesions or progression of any lesion.
- Stable disease (SD): Neither sufficient increase to qualify for PD nor sufficient shrinkage to qualify for PR.
- Progressive disease (PD): A 20% or greater increase in the sum of LD of all target lesions, taking as reference the smallest sum LD recorded at or following baseline.
- Once a patient reached PR or CR of his/her tumor assessment, another image will be done 4weeks later. A confirmed PR or CR is defined as both these image tumor assessment is in the same category (PR or CR).

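### Section 7.1 defines best response for the primary ORR as the last assessment before progression, which can turn a confirmed responder into a non-responder

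*Combined protocol and SAP*

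**What the plan says.** Table 1 in section 2 of the protocol sends the reader to section 7.1 for the definition of the phase II primary endpoint ("Refer to Section 7.1"). Section 7.1 counts a CR or PR as a response and then gives three sentences on best response, in this order:

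- The first names the governing standard: "The best response as defined by RECIST 1.1 will be used for ORR assessment".
- The second adds a definition of its own: "The best response is defined as the most proximal response assessment before disease progression".
- The third deals with patients who progress straight away: "If the first response evaluation showed disease progression, then the best response is PD".

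The same section sets the thresholds. PR is "A 30% or greater decrease in the sum of LD of all lesions in reference to the baseline sum LD". PD is a rise of at least 20%, "taking as reference the smallest sum LD recorded at or following baseline". Everything in between is SD. A PR or CR is re-imaged four weeks later, and it is confirmed if both scans fall in the same category.

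No other place supplies a best-response rule. The Synopsis says only "The objective response rate (ORR) based on RECIST 1.1". Section 6.3.1, item 4, repeats the categories and the confirmation rule ("A confirmed PR or CR is defined as both these image tumor assessment is in the same category (PR or CR"). Section 8.2.1 promises descriptive statistics and confidence intervals and does not say who counts as a responder.

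**The concern.** The assessment most proximal to progression is the one nearest to it, so the second sentence describes a last-response rule under the name of best response. It directly follows a sentence that invokes a different rule. Two analysts who both follow section 7.1 could therefore report different numerators for the primary endpoint.

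The decisions turn on single patients. At the first stage it is 0 versus 1 responder among 13 (sections 4.3 and 8.1). At the end it is 3 versus 4 among 27, a cut-off that follows from the stated design although the protocol does not print it. The trial is open-label and response is assessed by the investigator (sections 4.1 and 6.3.2), so choosing between the two readings after the responses are known would be a data-driven choice.

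The sentence is also incomplete. A patient without progression at data cut-off has no assessment before progression, and such patients may include the most durable responders.

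**Working it through.** **1. The stated design.** Inputs from section 8.1: P0 = 5%, P1 = 20%, type I error 0.05, power 80%, minimax two-stage design, 13 patients at stage 1 (stop at 0 responses), 27 evaluable, 10% drop-out. Sidedness is not stated and is taken as one-sided.

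With X₁ ~ Bin(13, p) and X₂ ~ Bin(14, p), the probability of success is

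Σ over x = 1 to 13 of P(X₁ = x) · P(X₂ ≥ 4 − x).

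An exact search finds 27 as the smallest total sample size. Among the designs of that size, 0/13 then 3/27 has the lowest expected sample size under P0 (19.81). It needs at least 4 responders of 27, with type I error 0.0416 and power 0.8011. Drop-out: 27 / (1 − 0.10) = 30. The plan's figures reproduce.

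**2. Can a responder be SD just before PD?** Set the baseline sum of diameters at 100. An SD reading after PR needs a sum above 70 (no longer PR) and below 1.2 × nadir (not yet PD). Both can hold only if 1.2 × nadir > 70, so the nadir must exceed 70 / 1.2 = 58.3. It must also be at most 70 to be a PR at all. The width of the SD band is 1.2 × nadir − 70:

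| Nadir | SD band above 70 |
|---|---|
| 70 | 14 points |
| 65 | 8 points |
| 60 | 2 points |
| 58.3 | none |

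**3. Worked patient**, on the protocol's imaging schedule plus the four-week confirmation scan:

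| Week | Sum | Against baseline | Against nadir 65 | Category |
|---|---|---|---|---|
| 8 | 65 | −35% | – | PR |
| 12 | 66 | −34% | 66/65 = 1.02 | PR, confirmed |
| 16 | 75 | −25% | 75/65 = 1.15 | SD |
| 24 | 80 | −20% | 80/65 = 1.23 | PD |

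On the ordinary meaning of *best*, this patient is a responder. Under the literal sentence the best response is SD.

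**4. Illustration of size.** The documents do not say how many responders would be affected. Assume that a share f is lost, independently between patients, and that the stage 1 gate counts any response. Let T ~ Bin(13, p) be the true stage 1 responders. The trial continues if T ≥ 1, counts K ~ Bin(T, 1 − f) of them, and adds Bin(14, p(1 − f)) from stage 2. Success is a counted total of at least 4.

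| f | Success probability at p = 0.20 | Success probability at p = 0.05 |
|---|---|---|
| 0 | 0.8011 | 0.0416 |
| 2% | 0.7882 | 0.0391 |
| 5% | 0.7675 | 0.0355 |
| 10% | 0.7291 | 0.0300 |

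If the literal rule also governs the gate, p is replaced by p(1 − f) throughout. Power is then 0.7872, 0.7649 and 0.7242 for f = 2%, 5% and 10%. The chance of a futility stop at a true ORR of 20% rises from 0.80¹³ = 0.055 to 0.81¹³ = 0.065 at f = 5% and 0.82¹³ = 0.076 at f = 10%.

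The borderline case can be isolated. At p = 0.20 the probability of passing the gate and finishing with exactly 4 true responders is 0.1563. Multiplying by 1 − (1 − f)⁴, the chance of losing at least one of the four, gives 0.0121, 0.0290 and 0.0538 for f = 2%, 5% and 10%. The expected number of responders is 27 × 0.20 = 5.4.

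**The case against.** The best counter-argument is that section 7.1 names RECIST 1.1 as the standard in its title, in the definition of ORR and in the sentence just before the disputed one. The sentence after it, on progression at the first evaluation, fits a reading in which progression merely closes the window of eligible scans. On that view the disputed sentence is a clumsy gloss, and nothing says that a later SD revokes a confirmed response. The exposed group is also narrow: partial responders with best shrinkage from 30% to just under 41.7%, and only if the last scan before PD falls in the SD band. Progression by a new lesion, or growth past the band between scans, avoids the problem. The power figures rest on an assumed f and a cut-off that the protocol does not print. A conservative wording conflict, it can be said, deserves a lower rating.

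Much of this stands. The intent may well have been right, the group is narrow, and the literal rule does not inflate type I error. It does not rescue the text. The specific definition follows the general reference and departs from it, and section 7.1 never says that a confirmed response overrides the last assessment. An analyst who applied the sentence would not be misreading the protocol.

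Two practical objections also stand and bear on the remedy. A bare ranking of CR, PR, SD and PD leaves out patients without a post-baseline scan. And with version 5.0 dated 2022-05-10, the 13-patient gate may already have been applied; the documents do not report accrual.

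**Conclusion.** The concern holds. The only operative definition of the primary endpoint contains a best-response rule that is wrong as written, contradicts the sentence before it, and is silent on patients who have not progressed. The worked patient needs no assumption beyond the protocol's own thresholds and schedule.

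The size is unknown and may be small. The power loss of 1.3, 3.4 and 7.2 percentage points (80.1% to 78.8%, 76.8% and 72.9%) is an illustration that depends on the assumed f of 2%, 5% and 10%, on independent losses, and on the derived cut-off of 4 of 27. The error is conservative: it can lower the ORR and the power, while type I error falls. The point is rated as a must-fix because a stated primary-endpoint rule is wrong, not because of the illustrated power loss.

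**What to change.** Delete the sentence and replace it with a rule such as: best overall response is the best category (CR, then PR, then SD, then PD) recorded from treatment start until progression, or until the last assessment if the patient has not progressed. In the same amendment:

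- State that the same responder definition applies at the 13-patient gate and at the final analysis. If the gate has already been applied, record which definition was used there.
- State whether the ORR counts only responses that meet the confirmation rule already in section 7.1. That choice is the sponsor's.
- State how patients without a post-baseline scan are classified.

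The sample size does not change, and no new scans or patients are needed, because the change only says which recorded category is counted. The cost is a dated amendment or SAP entry. It should be in place before the response analysis: relative to the literal rule the replacement can only add responders, the trial is open-label, and version 5.0 already comes late against the 2022/12/13 timeline in section 4.3.
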